5.5 Handling of Missing, Unused, and Spurious Data

Except for the below specified, missing data will not be imputed.

5.5.1 Annualized Bleeding Rate

For all subjects who prematurely discontinued from the study (i.e., before ObsDay 364), and who refuse to provide data on bleeds for the remaining time till ObsDay 364, the number of bleeds (and hence the ABR), will be imputed for the second 6-month period, using Multiple Imputation techniques as described below. The ABR for a subject is calculated as the number of bleeds divided by the observation period under consideration (expressed in years).

The number of bleeds during the missing observation period in PROPEL, will be imputed for subjects taking into account, additional post-PROPEL bleeding information that is provided for the subject. Post-PROPEL bleeding information obtained for a subject (either by the subject or from another BAX 855 study), will be treated as if observed within PROPEL before the imputation procedures.

For simplicity, the imputation process is described below for a single subject (since the imputation will be performed on a subject specific basis), focussing on the period of interest for the primary endpoint (2nd 6-month period). The imputation process is described in step-by-step manner.

5.5.1.1 Primary Endpoint Imputation

The unobserved period (which is subject specific), is defined as the subject's missing observation period in PROPEL for which there is no post-PROPEL bleed information provided.

Step1: Fitting the model

- A subject specific Negative Binomial model will be fitted. The dependent variable (left-side of the model equation), is the number of bleeds in the subject's unobserved period after ObsDay 182, taken from all subjects in the same treatment arm (low level or high level), as the subject being imputed. The offset will be the logarithm of the duration (in days), of the unobserved period for the subject (LUP). Covariates (model variables) will be stratum category, race, age at baseline and total number of bleeds observed per subject (OB), calculated for all subjects in the same treatment group of the subject for imputation.

- It is desired to avoid using bleeds in the endmost observation period as part of the covariates since the number of bleeds observed in other subjects at that time might be very low or even zero. Therefore OB, is measured in the range from ObsDay 92 up to the minimum of:
 - Last ObsDay for subject being imputed.
 - ObsDay 329.
- The following example SAS[®] code can be utilized:

```
Proc Genmod Data = <Dataset>;  
  Class <Stratn> <Racen>;  
  Model <UB> = <Stratn> <Racen> <BAge> <OB> / Dist = Negbin  
    Offset = <LUP> Link = log;  
  ODS Output ParameterEstimates = <Outdata>  
Run ;
```

Where <Dataset> represents the input dataset containing all subjects in the same treatment arm as the subject being imputed, who have at least the same amount of ObsDays as the subject being imputed. <UB> represents the number of bleeds during the subject's unobserved period (up to the maximum of ObsDay 329), <Stratn> is the numeric stratum category, <Racen> the numeric race category, <BAge> the age at baseline, <OB> and <LUP> as defined above and <OutData> the output dataset containing the parameter estimates.

Step2: Predicting the Poisson Parameter and Imputing with it

- The subject-specific Poisson parameter will be predicted from the above model fitting results by using the predicted mean number of bleeds during the subject's unobserved period (Mu) as the prediction for the Poisson parameter.
- The number of bleeds for the subject to be imputed, will be for the "imputation period" (days), where the imputation period is defined as:

Imputation Period (days) = (Date Corresponding to ObsDay 364 – Imputation Start Date)

Where imputation start date is as defined in section 5.4.2: Extended Observation Period of Efficacy.

- This “imputation period” will be treated/imputed as a Poisson random variate. The following example SAS[®] code can be utilized to obtain an estimate for the Poisson parameter:

```
Data <ImpSet>;  
  Set <Dataset>;  
  
  <Mu> = exp(1*<Intcpt> + <Beta1>*<sStrat> + <Beta2>*<sRace> +  
            <Beta3>*<sBAge> + <Beta4>*<sOB> + <LIP>);  
  Do i = 1 to 1 000  
    <ImpUB> = Ranpoi(1234,mu);  
    Iteration = i;  
    Output;  
  End;  
Run;
```

Where <Impset> represents the resultant dataset containing the 1 000 imputed bleed count values. <Dataset> is the input dataset containing the parameter estimates obtained from fitting the Negative binomial as discussed above and <Mu> our Poisson parameter as defined above. <Beta1>, <Beta2>, <Beta3> and <Beta4> the parameter estimates for <Stratn>, <Racen>, <BAge> and <OB> respectively. <sStratn>, <sRacen>, <sBAge> and <sOB> hold values specific to the subject being imputed, for numeric stratum category, numeric race category, baseline age and observed bleeds from ObsDay92 till last ObsDay for the subject, respectively. <LIP> is the logarithm of the imputation period (days) for the subject being imputed and <ImpUB> is the imputed number of bleeds during the imputation period for the subject.

Step3: Adding of Imputed Values to the Observed Values

The imputed bleed count of the subject is added to the subject’s observed bleed count (i.e. the subject’s observed bleeds after ObsDay 182), to obtain a bleed count for the complete 2nd 6-month period of the subject.

$$\text{Complete period bleeds} = \text{Observed period bleeds} + \text{Bleeds for imputation period}$$

For each subject to be imputed, the 1 000 imputed values will be merged into the full subject dataset, thus creating 1 000 replicates of imputed (complete) data sets (one for each imputation iteration).

Step4: Calculating ABR and Categorization

From this step onward we are working with all the subjects (those imputed and those not needing imputation) in the same dataset (1 000 replicates of them).

ABR is calculated as:

$$ABR = \frac{(Observed\ Number\ of\ bleeds + Imputed\ number\ of\ bleeds)}{Period\ under\ consideration\ in\ years}$$

Where period under consideration is:

- 1 year (365.2425 days) when working with the full year.
- 0.5 years (182 days) when working with the second 6-month period.

For presentations using unimputed ABR:

$$Unimputed\ ABR = \frac{Number\ of\ bleeds\ observed\ within\ PROPEL}{Period\ under\ consideration\ in\ years}$$

A numeric categorical variable for imputed ABR during the complete planned treatment period will be derived as follows:

- Category 1: ABR = 0.
- Category 2: ABR > 0.

Step5: Analysis of Imputed Data Sets

Chi-squared statistics with continuity correction should be calculated for each of the thousand complete datasets on the ABR categorical variable with treatment arm as fixed effect. The following SAS® code can be used:

```
Proc Freq Data = <Dataset>;  
  By <Iter>;  
  Tables <ABRCat>*<Trt> / chisq alpha = 0.05 relrisk riskdiff expected;  
  exact or;  
  Ods Output Chisq = <Outdata>;  
Run;
```

Where <Dataset> is the input dataset containing the 1 000 iterations of the completed

data, <Iter> the iteration number, <ABRCat> the numeric ABR category variable, <Trt> the treatment arm and <Outdata> the output dataset containing the continuity adjusted chi-squared statistics.

Step6: Combining of Statistical Results

An approximately Gaussian test statistic will be derived as the square root of the chi-squared statistic with continuity correction and 1 degree of freedom, with the sign set according to the direction of the effect (proportion higher in treatment arm one [High level] than in treatment arm two [Low level]; zero if equal). That is, if the risk difference of the High Level Arm minus the Low Level arm provided by SAS[®] is larger than naught then the sign to retain will be positive and vice versa.

This needs to be done so the requirements of Rubin's rules are met and the SAS procedure PROC MIANALYZE can be used.

The resultant 1 000 approximately Gaussian test statistics will be summarized using the SAS[®] procedure MIANALYZE. SAS[®] code similar to the below can be utilized:

```
Proc MIanalyze data=<Dataset>;  
  Modeleffects <NormStat>;  
  Stderr <NormSterr>;  
  Ods Output ParameterEstimates = <Outdata>;  
Run ;
```

Where <Dataset> represents the input dataset containing the approximately Gaussian statistics, <NormStat> and <NormSterr> the approximately Gaussian statistics and standard error of 1 respectively and <Outdata> the output dataset containing the overall estimate, 95% confidence interval and corresponding P-value.

Step7: Back Transformation

The resulting overall estimate and 95% confidence interval should be back transformed (due to using a logarithmic link function when fitting the Negative Binomial model), by applying the following calculation:

$$\text{BackTransformed value} = \exp[(\text{Value})]$$

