2.3 Sample Size and Power Calculations

For the sample size assessment the following assumptions were used. Approximately 40% of subjects in BAX 855 regimen targeting 1-3% trough level are expected to be bleed-free as shown in the ADVATE Prophylaxis study and the BAX 855 pivotal study 261201. For the BAX 855 regimen targeting approximately 10% (8-12%) trough level, an increase to 70% bleed-free subjects is expected based on modeling the bleeding rates per FVIII level in the BAX 855 pivotal study 261201.

Under these assumptions 48 subjects per study arm are needed to reject the null hypothesis of no difference between the study arms against a two-sided alternative at the 5% level of statistical significance with 80% power. Assuming a drop-out rate of close to 10%, and 10-15% of subjects being non-compliant, approximately 116 subjects are planned to be randomized between the two BAX 855 regimens with an allocation ratio of 1:1.

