5.12 Examination of Subgroups

The following subgroups will be utilized in analyses as indicated in the latest version of the Output Templates as well as the various sections to follow:

- Stratum, as derived from the pre-study ABR and pre-study treatment type, captured on the Hemophilia A Treatment History eCRF panel:
 - Pre-study prophylaxis treatment with $ABR < 5$.
 - Pre-study prophylaxis treatment with $ABR \geq 5$.
 - Pre-study on-demand treatment.

- Age groups (years) (per different regulatory standards, resulting in overlapping groups), using age at informed consent as obtained from the Demographics eCRF panel:
 - European Medicines Agency (EMA):
 - European (EU) Age Group ≥ 12 to < 18 .
 - EU Age Group ≥ 18 .
 - Food and Drug Administration (FDA):
 - United States (US) Age Group ≥ 12 to < 17 .
 - US Age Group ≥ 17 .
- Race as obtained from the Demographics eCRF panel:
 - Asian.
 - Black or African American.
 - Native Hawaiian or other Pacific Islander.
 - White.
 - Other.

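### The imputation model refitted for each leaver rests on very few bleeds for late leavers, on none from ObsDay 329, and can impute leavers in sparse categories as bleed-free

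*SAP*

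**What the plan says.** SAP 5.5.1.1, Step 1, fits a separate negative binomial model for every imputed subject. The fitting set is the same arm, restricted to subjects with at least as many observation days as the leaver.

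- **Outcome:** their bleeds in the leaver's "unobserved period (up to the maximum of ObsDay 329").
- **Covariates:** "Covariates (model variables) will be stratum category, race, age at baseline and total number of bleeds observed per subject (OB"). The example code declares stratum and race as class variables; age and OB are continuous.
- **OB** "is measured in the range from ObsDay 92 up to the minimum of" two days: the leaver's last ObsDay and ObsDay 329.

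SAP 5.12 lists three strata and five races, one of them "Native Hawaiian or other Pacific Islander". SAP 6.2 adds a Mixed category, for summaries only.

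Steps 2 to 4 use the predicted mean as a Poisson parameter, draw 1,000 counts, add them to the observed bleeds after ObsDay 182, and classify ABR as zero or above zero.

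Protocol 14.4.1 has the same covariates and the same Day 92 start. For subjects with more than 21 weeks in the period it switches to a model of bleeds up to Day 329, expressly to avoid instability.

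Neither document says what to do about non-convergence, a category with no bleeds, an empty outcome window or an empty OB window.

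**The concern.** This model decides the primary endpoint for every leaver who supplies no later bleed data. Four features of the written rule cause trouble.

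- The later a subject leaves, the shorter the window, so the same covariate list is fitted to fewer and fewer bleeds.
- From ObsDay 329 the window has zero days.
- A sparse class level with no bleeds sends its coefficient to minus infinity. A leaver in that level then gets a predicted mean of zero and counts as bleed-free, which is the favourable outcome.
- OB starts at ObsDay 92. For a leaver before then it is an empty count, and that subject's recorded bleeds play no part.

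Without a stated rule, any repair would be chosen after the data are seen, in an open-label trial and on the primary analysis.

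**Working it through.** **1. The plan's own figure.** SAP 2.3 gives no figure for the imputation model, only for the sample size. Its inputs are "Approximately 40% of subjects in BAX 855 regimen targeting 1-3% trough level are expected to be bleed-free", "an increase to 70% bleed-free subjects is expected" and "against a two-sided alternative at the 5% level of statistical significance with 80% power". The usual two-proportion formula with continuity correction gives 49 per arm, and the exact power of the corrected chi-square at 48 per arm is 0.800. So "48 subjects per study arm are needed" is reproduced. The 116 randomized make 58 per arm.

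**2. Parameters.** Intercept 1 + stratum 2 + race 4 + age 1 + OB 1 + dispersion 1 = 10. If Mixed enters the model, 11.

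**3. Mean bleeds per 182 days**, solved from the assumed bleed-free share p.
- No overdispersion, m = -ln(p): high arm -ln(0.70) = 0.357; low arm -ln(0.40) = 0.916.
- Dispersion k = 1.6 (assumed), m = (p^-k - 1)/k: high 0.481; low 2.083.

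**4. Expected bleeds in the fit** = m/182 x (329 - last ObsDay) x 52. The 52 is an assumption: 58 less about 10% dropout. Example, high arm, ObsDay 300: 0.357/182 x 29 x 52 = 3.0.

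| Last ObsDay | Days in window | High, k = 0 | High, k = 1.6 | Low, k = 0 | Low, k = 1.6 |
|---|---|---|---|---|---|
| 260 | 69 | 7.0 | 9.5 | 18 | 41 |
| 300 | 29 | 3.0 | 4.0 | 7.6 | 17 |
| 315 | 14 | 1.4 | 1.9 | 3.7 | 8.3 |
| 329 or later | 0 | none | none | none | none |

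**5. Early leavers.** For a last ObsDay up to 182, the window is 147 days (to ObsDay 329) or 182 days (to ObsDay 364). With 48 per arm and k from 0 to 2, the fit holds 36-126 bleeds in the low arm and 14-25 in the high arm. For a last ObsDay of 91 or earlier, OB is zero for everyone in the fit and cannot be separated from the intercept. For leavers on Days 92-182, only the Day 1-91 bleeds are dropped.

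**6. Levels without bleeds.** Simulation: 200 arms of 52 per setting, k = 0, 1 or 2, two assumed race mixes, one assumed stratum mix, no true covariate effects. It counted fits with no finite estimate for at least one coefficient.
- Leaver at ObsDay 320, window to 329: 98-100% (low arm) and 100% (high arm).
- Leavers up to ObsDay 182, window to 329 or 364: 21-65% (low) and 67-91% (high), mostly from sparse race levels.

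For a leaver in such a level the mean tends to zero. Multiplying it by 1.1 to 1.8 leaves it near zero.

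**7. Size.** Planned leavers: 58 x 10% = about 6 per arm. For a Day 320 leaver with no bleed so far, the chance of a bleed in the missing 44 days is 1 - exp(-0.357 x 44/182) = 8% (high) or 1 - exp(-0.916 x 44/182) = 20% (low). A leaver missing the whole period and wrongly imputed as bleed-free shifts the arm's proportion by 0.30/58 = 0.5 percentage points (high) or 0.60/58 = 1.0 point (low).

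**The case against.** **Late leavers matter least.** They have the fewest days left to impute, and early leavers, who have the most, get fits with more than a handful of bleeds. This stands, though the high arm remains thin at every leaving day.

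**Few classifications depend on the model.** Post-study bleed data from the continuation study or the subject are treated as observed (SAP 5.5.1, 7.1.2.1, 7.1.2.2). Anyone who has already bled after ObsDay 182 is above zero whatever is imputed. This also stands.

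**Separation is local.** A level without bleeds distorts predictions for leavers in that level, not for the others. The simulated percentages are therefore not the share of imputations that fail.

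**Other analyses exist.** The worst-case analysis and the per-protocol comparisons do not use this model. However, SAP 7.1.2 refers the worst case to Section 5.5, which does not define it; only Protocol 14.4.1 describes it, in general terms.

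**The Protocol foresaw instability.** Since 182 + 21 x 7 = 329, its clause covers the leavers for whom the SAP window is empty. If it means all bleeds from Day 183 to 329, the fit holds 14-20 (high) or 36-102 (low) bleeds. But the Protocol does not say where that count starts, and on this reading its Day 92-329 covariate would contain the outcome. The SAP instead applies Day 329 as a cap for every leaver, which shortens the windows.

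**Stronger readings that the documents do not support.** A reader might infer that the model is uninformative for early leavers. It is not: stratum, which carries pre-study regimen and ABR, stays in with age and race, and bleeds from ObsDay 92 are used. Nor do the documents say that early leavers go because of bleeding. Starting at ObsDay 92 is also defensible in itself, because Protocol 8.7.6 lets doses be adjusted on trough levels during the first six months.

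**Conclusion.** The concern holds in limited form. Followed as written, Step 1 gives a model with about as many parameters as bleeds, or fewer bleeds than parameters, for high-arm leavers from about ObsDay 260 and for many later low-arm leavers. It gives no model from ObsDay 329. It can impute a leaver in a sparse level as bleed-free, more readily in the high arm, and the inflation analyses would not reveal this. It uses no on-study bleeds for leavers up to ObsDay 91.

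It does not follow that the imputation fails generally. In the simulations, 35-79% of low-arm fits for leavers up to ObsDay 182 had finite estimates throughout. With about 6 leavers per arm, fewer after post-study data, the effect on the primary comparison is small beside the planned 30-point difference. This should be corrected, but it does not undermine the design.

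The figures rest on the SAP's 40% and 70% bleed-free shares, and on assumed fit sizes (48 or 52), dispersion, and race and stratum mixes.

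**What to change.** In SAP 5.5.1.1:

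- Fit one negative binomial rate model per arm to all observed second-period time (ObsDay 183-364), with offset log(days observed), and predict each subject's missing days from it. This works for any leaving day.
- Collapse sparse race levels to White / other.
- Enter prior bleeding as a rate with its exposure, counted from ObsDay 1 for subjects who left before ObsDay 92. State where that window ends, so that it does not overlap the modelled period.
- Pre-state a fallback, for example dropping race, if the fit does not converge or a level has no bleeds.

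Reconcile this with the Day 329 clause in Protocol 14.4.1. The covariates and the Day 92 start come from the Protocol, so list the change in SAP 5.8; it is more than SAP wording.

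Cost: the code becomes simpler. Race enters more coarsely, which slightly weakens the reason the Protocol gives for including it, namely subgroup analyses. The high-arm fit stays thin: intercept 1 + stratum 2 + race 1 + age 1 + prior rate 1 + dispersion 1 = 7 parameters on about 17-25 bleeds with 48 subjects, against 44-126 bleeds in the low arm. The fallback is therefore needed even with the better model.

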14.4 Methods of Analysis

14.4.1 Primary Outcome Measure

The proportion of subjects with ABR = 0 in the 2 prophylaxis treatment regimens in the second 6 months period will be compared using a chi-square test with continuity correction at a 2-sided 5% level of significance.

The null hypotheses of no difference between the prophylactic regimens will be tested against a 2-sided alternative.

The observation period for the primary endpoint will be the second 6 months of prophylaxis (Day 183 to Day 364). If the subject undergoes a surgical procedure the observation period is interrupted starting from the presurgical loading dose until the subject resumes his previous prophylactic treatment regimen, or until rehabilitation or any other surgery specific postoperative measures have been completed, whichever occurs last.

Data analyses will follow the intent-to-treat principle, i.e., bleedings observed in the observation period will be used in the analyses irrespective of compliance with the treatment regimen of the protocol. Only if a subject refuses to provide any bleeding data, the multiple imputations (MI) technique will be used to handle observation periods shorter than 6 months, i.e., 182 days, as follows.

For subjects who terminated before Day 364 and refuse to provide data on bleeds, bleeds will be imputed for the unobserved period from a Poisson random variate. The subject specific Poisson parameter will be determined from estimating a negative binomial model for the bleed rate in the unobserved period with stratum, age, race as well as the number of bleeds from Day 92 to the end of the observed period of the subject as covariates in all subjects of the same Study Arm. For subjects with more than 21 weeks in the observation period, the number of bleeds occurring at a later time in other subjects might be very low or even zero. To avoid estimating from an unstable model, the negative binomial model will be for the number of bleed up to Day 329 with covariates of stratum, age, race and number of bleeds observed from Day 92 to Day 329. At least 1000 imputation datasets will be generated. The chi-squared test statistics with continuity correction and its standard error will be used to compare the 2 study arms in each imputation dataset and the multiple imputations techniques will be used to derive an overall estimate with 2-sided 95% CIs.

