5.5.1.2 Sensitivity Analysis

For the sensitivity analyses, the same imputation procedure as described above will be applied with the Poisson parameter being artificially increased by 10%, 20%, 40% and 80% for all subjects imputed, regardless of their respective treatment arm. Imputation will also be performed as described in Steps one through seven, but with the post-PROPEL bleed data removed.

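### The primary-endpoint imputation model credits early leavers, used as donors, with follow-up they did not have, so fitted bleed rates are slightly too low

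*SAP*

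**What the plan says.** SAP 5.5.1.1, Step 1, fits a separate model for each subject to be imputed.

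- **Response:** the number of bleeds in that subject's "unobserved period after ObsDay 182, taken from all subjects in the same treatment arm (low level or high level".
- **Donors:** same-arm subjects "who have at least the same amount of ObsDays as the subject being imputed".
- **Exposure:** "The offset will be the logarithm of the duration (in days), of the unobserved period for the subject (LUP". The example code passes this one value as the offset.
- **Cap:** the counted bleeds run "up to the maximum of ObsDay 329".

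Protocol 14.4.1 is less specific. It describes "estimating a negative binomial model for the bleed rate in the unobserved period with stratum, age, race" and certain bleed counts "as covariates in all subjects of the same Study Arm". It states neither a donor rule nor an offset.

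Two other provisions bear on the point. Under SAP 5.5.1, post-study bleed data "will be treated as if observed within PROPEL before the imputation procedures". Under SAP 5.5.1.2, the sensitivity analyses repeat the imputation "with the Poisson parameter being artificially increased by 10%, 20%, 40% and 80% for all subjects imputed, regardless of their respective treatment arm".

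**The concern.** The donor rule guarantees that a donor was followed up to the imputed subject's last day. It does not guarantee follow-up through the window being modelled, which starts after that day. Suppose the imputed subject was last seen on ObsDay 200 and a donor on ObsDay 220, with no later data. The donor's bleeds can be counted for 20 days, but his exposure is set at 164 days (ObsDay 201 to 364). The other 144 days are treated as observed and bleed-free.

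Reading the offset as donor-specific does not rescue the text. A completer has no unobserved period, so the log of its duration is undefined. Nothing in the SAP sets a partly observed donor's count to missing or shortens his exposure.

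At stake is the imputed chance of a bleed in the primary analysis. SAP 5.5.1.3 carries the same procedure over to the secondary bleed endpoints.

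**Working it through.** **Inputs from the documents.** 58 per arm (Protocol 8.1); bleed-free 40% and 70%, dropout close to 10% (SAP 2.3); primary window ObsDay 183-364, 182 days (SAP 7.1).

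**Assumptions not in the documents.** Leaving days uniform over 1-363; no leaver gives post-study data; constant individual bleed rate. For a subject who leaves before ObsDay 183, the offset is taken as the 182-day window, to match the count.

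**The plan's own figure.** The documents give no figure for the imputed rates. The sample size that supplies the 40% and 70% reproduces: the continuity-corrected formula gives 49 per arm against the stated 48, and power at 48 is 79.6%.

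**Bias formula.** With a constant offset and an intercept-only model, fitted rate / true rate = the donors' mean observed fraction of the window. Let d be the proportion of leavers and L the imputed subject's last day.

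- Later leavers with some observed days: q = d x (363 - max(L, 182))/363. On average they are observed for about half the window.
- Donors who left after L but before ObsDay 183: r = d x (182 - L)/363 when L < 182, otherwise 0. They have no observed day in the window.
- Factor = (1 - d + q/2)/(1 - d + q + r). If donors with no observed day drop out as missing, r is omitted.

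**Numbers put in.**

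- L = 182, d = 0.10: q = 0.10 x 181/363 = 0.0499; (0.90 + 0.0249)/0.9499 = 0.974.
- L = 182, d = 0.25: q = 0.1247; (0.75 + 0.0623)/0.8747 = 0.929.
- L = 92, d = 0.10: r = 0.10 x 90/363 = 0.0248; 0.9249/0.9747 = 0.949.
- L = 92, d = 0.25: r = 0.0620; 0.8123/0.9367 = 0.867.

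**Mean shortfall over all leavers** (simulated arms of 58):

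| Reading | 10% leavers | 25% leavers |
|---|---|---|
| Donors with no observed day dropped as missing | 2.0% | 5.4% |
| Those donors kept with a zero count | 3.3% | 8.5% |
| Imputed subject also his own donor | 5.0% | 10.4% |

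**Effect on the bleed-free proportion.** With a Poisson draw, a shortfall s turns a bleed-free probability p into p^(1-s). For s = 10%, 0.40^0.9 = 0.438 and 0.70^0.9 = 0.725: 3.8 and 2.5 points for one subject imputed over the whole window. Only leavers are imputed, so the effect on an arm is far smaller.

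A fuller simulation (log-link negative binomial with the observed-bleed covariate, imputed subject allowed as his own donor, 150 runs of 40 imputations) compared the SAP rule with donor-specific offsets:

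- 10% dropout: an arm's bleed-free proportion rises by 0.13-0.19 points (for example 0.4043 to 0.4062).
- 25% dropout: it rises by 0.64-0.95 points.
- Equal dropout: the high-minus-low difference falls by 0.02-0.20 points.
- Low/high dropout 10%/25% or 5%/25%: the difference rises by 0.46-0.62 points and mean z by 0.05-0.07.

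That simulation's rate shortfalls were larger (7-21% at 10% dropout, 14-18% at 25%). They include self-donation and are unstable: with 10% dropout in both arms and dispersion 1, the ratios were 0.906 and 0.786. They are not used for the size.

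**Interaction with the cap.** Counting bleeds to ObsDay 329 against an offset that runs to ObsDay 364 is a separate and larger mismatch in the same step: 147/182 = 0.81 for a window from ObsDay 183, and 56/91 = 0.62 for a subject last seen on ObsDay 273.

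**The case against.** **The literal reading is stretched for some donors.** A reader might infer that the imputed subject, and donors who left before ObsDay 183, enter with zero bleeds. The donor rule does admit them, but the SAP nowhere says that an unobserved count is zero, and SAP 5.5 rules out imputation beyond its listed exceptions. A wholly missing response would normally be dropped from the fit. This stands, so the 5% and 10% figures should not be the headline. It does not help the partly observed donor, whose count exists and whose exposure is wrong.

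**The effect is small and partly mitigated.** This also stands. Leavers who supply later data are not incomplete donors, whereas the calculation assumes that all refuse. The 25% scenario adds the separate non-compliance allowance to dropout, although SAP 7.1.2 uses recorded bleeds regardless of compliance. The inflation runs of 10% to 80% cover a shortfall of this size, a worst-case run is planned, and bleed-rate comparisons are also shown in the per-protocol set, which requires completion. The inflation is the same in both arms, however, so it does not remove an arm imbalance.

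**The direction between arms is not general.** A reader might infer that the bias always favours the arm that loses more subjects. The figures above contradict this. The same shortfall moves an imputed low-arm subject by 3.8 points and a high-arm subject by 2.5, so at equal dropout the bias runs slightly against the high-trough arm. With 10% low-arm dropout, the sign turns only at about 12% in the high arm.

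**Conclusion.** The rule as written biases the fitted bleed rate low whenever a partly observed donor is in the fit, and no other provision corrects it. Under the stated assumptions the mean shortfall is about 2-3% at 10% leavers and 5-9% at 25%, less if leavers supply post-study data. The effect on an arm's bleed-free proportion is about 0.1-0.2 points at the planned dropout and up to about 1 point at 25%, against a planned difference of 30 points.

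The rate shortfall is larger in the arm with more incomplete donors only if leaving times and refusal rates are similar across arms. The net effect on the comparison also depends on each arm's bleed rate. The documents do not support a claim that the trial's conclusion is at risk. They do support correcting a pre-specified primary-analysis rule that is wrong and almost free to repair.

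**What to change.** In SAP 5.5.1.1, Step 1, replace the common offset with a donor-specific one: the log of the days that donor was observed within the window over which bleeds are counted.

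- **Start:** the later of ObsDay 183 and the day after the imputed subject's last ObsDay.
- **End:** the earlier of the donor's last observed day (post-study data included) and the end of the counted window, which is ObsDay 329 if the count is capped there.
- **Exclude:** the imputed subject, and any donor with no observed day in that window.

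Alternatively, restrict donors to those observed to the end of the counted window and use that window's length as the offset. In simulation the two agreed within about 1.5%.

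The ObsDay 329 cut matters: without it, either version would leave the larger cap mismatch in place. For a subject last seen on or after ObsDay 329 the capped window is empty, so the text should also name the window to be used there.

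Cost: one derived variable and one line of SAP text. No new data are needed.
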